## STUDY SCHEMA

**STUDY SUMMARY**

Title	e-Motivación: Developing and Pilot Testing an App to Improve Latinos' Screening Colonoscopy Rates: Aim III
Short Title	N/A
Protocol Number	IRB-18-00344
Phase	N/A
Methodology	Pilot Randomized Control Trial
Study Duration	9 months to conduct pilot study, 6 months to analyze pilot study data and disseminate results.
Study Center(s)	Single-center
Objectives	To begin to examine the efficacy of the e-Motivación app for improving screening colonoscopy uptake among Latinos (results of the pilot study will inform power calculations for a future randomized clinical trial that will formally test the efficacy of the app).
Number of Subjects	80 subjects total (N=40 in control group, N=40 in condition group)
Diagnosis and Main Inclusion Criteria	
 
1. Self-identified as Latino,a,x
 
2. English or Spanish-speaking
 
3. Received a physician referral for a screening colonoscopy
 
4. Has access to a tablet, smartphone, or computer with working internet
 

Study Product(s), Dose, Route, Regimen	N/A
Duration of administration	N/A
Reference therapy	N/A
Statistical Methodology	Contingency tables and t-tests will be performed to determine any differences between the two groups. Using a p value of $\leq 0.15$ , any consistent pattern of correlation for any of the covariates would suggest their inclusion in the primary data analysis model. Effect size estimate: Logistic regression analyses will be used to evaluate an estimate of the efficacy. The model will include any covariates that differentiate the intervention and control groups. The effect size of the treatment group will be used as an indicator to inform power calculations for a future RCT. The power calculations will inform the appropriate sample size needed for the RCT.

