**Motivational Interviewing.** Motivational Interviewing (MI), a brief client-centered behavioral intervention, may improve Latinos' screening colonoscopy uptake. Drawing from Self-Determination Theory (SDT), MI helps increase competence, autonomy, and relatedness in order to promote behavioral change. MI involves four sequential processes: (1) *engaging* the patient in the intervention; (2) *focusing* the goal of the intervention; (3) *evoking* motivations for change; and, (4) *planning* for change. Within this framework, MI implements techniques (e.g., decisional balance) to support behavior change. MI was originally developed to treat substance use, and extensive research supports its efficacy for treating drug, alcohol, and nicotine use. More recently, MI has proven efficacious for improving health behaviors such as diet, exercise, and medication adherence. A meta-analysis found that MI had a significant, moderate effect ( $d=0.53$ ) for improving health behaviors when compared to a no treatment/placebo control group. Moreover, research has found that the effects of MI are long-lasting (>2 year follow up). Extensive evidence supports the use of MI with Latinos. For example, research with exclusively or predominantly Latinos/Hispanic samples have found MI efficacious for managing diabetes, decreasing drug use/needle sharing, quitting smoking, and decreasing alcohol use. In fact, a 2005 review found MI to yield larger effect sizes with minorities, compared to non-minority whites.

**MI for Colonoscopy.** Preliminary research has found MI to be efficacious for improving screenings for HIV, breast cancer, skin cancer, and cervical cancer. A recently published study examining the efficacy of MI to improve CRC screening uptake produced promising results, though non-significant ( $OR=1.6$ ,  $CI=0.9, 3.0$ ). Notable problems with this study may have limited the effects of MI. Most critical, not all MI interventionists were proficient in MI in the beginning stages of the study. Additionally, the intervention implemented techniques (e.g., discussing ambivalence when it was not clinically indicated) that may have been counterproductive. A systematic review of the literature yielded that

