eliminating errors in data entry and maximizing data security. **(3) Tailored by Language:** E-health interventions can be programmed to be offered in multiple languages (e.g., Spanish and English) to address a wide range of patient populations.

**e-MI to Improve Latinos' Screening Colonoscopy Uptake.** Despite the strong promise of MI for improving screening colonoscopy uptake, and the advantages of e-MI, no study to date has examined the efficacy of e-MI to improve Latinos' screening colonoscopy uptake. This study pilot tests an e-MI intervention, e-Motivación (e-Motivation), to help improve Latinos' screening colonoscopy uptake. This line of research will increase our understanding of efficacious interventions to improve Latinos' CRC screening rates. It will also provide power calculations for a future RCT that will formally examine the efficacy of the e-Motivación app for improving Latinos' screening colonoscopy uptake. This program of research can help increase Latinos' colonoscopy uptake and, in doing so, reduce CRC screening disparities.

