## 2.0 STUDY OBJECTIVES

### 2.1 Primary Objectives

2.1.1 To obtain an estimate of the efficacy of the e-Motivación app for improving screening colonoscopy uptake among Latinos  
[For details, please see section 5.2.2; a detailed flowchart of the App is attached – please see Appendix B]

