## 10.2 Sample Size and Accrual

The sample includes 80 participants: 40 in the e-Motivación condition arm and 40 in the control arm. Based on previous studies, this sample will provide a large enough sample to determine the effect of the intervention. We also expect the ratio of male to female participation to be 4 to 6.

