## 10.3 Data Analyses Plans

*Analyses of covariates:* Due to the use of randomization, significant baseline differences (e.g., gender, age) between condition and control groups are not expected. However, contingency tables and t-tests will be performed to determine any differences between the two arms. Using a  $p$  value of  $\leq 0.15$ , any consistent pattern of correlation for any of the covariates would suggest their inclusion in the primary data analysis model.

*Effect size estimate:* Logistic regression analyses will be used to evaluate an estimate of the efficacy. The model will include any covariates that differentiate the intervention and control groups. The effect size of the treatment group will be used as an indicator to inform power calculations for a future RCT. The power calculations will inform the appropriate sample size needed for the RCT.

*Missing data:* The e-Motivación app is a one-time intervention and the questionnaire to assess demographics and medical history of participants will be conducted as an interview. Therefore, we anticipate minimal missing data.

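### Section 10.2 calls 40 per arm large enough to determine the effect, which it is not, and section 10.3 carries that effect into the future RCT's power calculations with no allowance for its imprecision

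*Combined protocol and SAP*

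**What the plan says.** The only objective is in section 2.1: "To obtain an estimate of the efficacy of the" app. Sections 2.2 and 2.3 list no secondary or exploratory objectives. The endpoint is binary: colonoscopy completion in the chart six months after consent (section 2.4).

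The estimate has one stated use. The Study Summary says that "results of the pilot study will inform power calculations for a future randomized clinical trial that will formally test the efficacy of the app", and section 1.4 says of this work: "It will also provide power calculations for a future RCT that will formally examine the efficacy". Section 10.3, repeated under Statistical Methodology in the Study Summary, obtains the effect from logistic regression and continues: "The effect size of the treatment group will be used as an indicator to inform power calculations for a future RCT". Then: "The power calculations will inform the appropriate sample size needed for the RCT".

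The sample size of 40 per arm is justified in section 10.2 by one sentence: "Based on previous studies, this sample will provide a large enough sample to determine the effect of the intervention". No control rate, target effect, alpha, power or precision is given, and the previous studies are not identified.

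Section 1.1 gives two background effects. One colorectal screening trial of motivational interviewing "produced promising results, though non-significant" (OR 1.6, CI 0.9 to 3.0). For health behaviours in general, "A meta-analysis found that MI had a significant, moderate effect" (d = 0.53).

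**The concern.** Section 10.2 tells the reader that the pilot will settle the effect, and section 10.3 passes that effect on to the next trial's sample size. Nowhere do the documents ask for an interval around the estimate, a range of effects, a conservative bound, a worthwhile difference, or a rule for a null or very imprecise result.

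Sample size varies roughly with the inverse square of the assumed effect, so error in the pilot estimate is magnified in any size derived from it. The pilot's participants and data are unaffected. What is at stake is the pilot's one deliverable: a reader who trusts 10.2 would rely on the estimate more than the design allows, and the later RCT could be far too small or far too large.

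**Working it through.** **The plan's own figure.** The total of 80 cannot be reproduced, because no effect, control rate, alpha or power is stated. For orientation, OR 1.6 needs 288-520 per arm over the control rates below (two-sided 5%, 80% power), and power with 40 per arm is 12-18%. Treating d = 0.53 as a difference in means needs 56 per arm, and 40 per arm gives about 66% power.

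**Inputs.** From the documents: 40 per arm (10.2); binary endpoint (2.4); OR 1.6 and d = 0.53 (1.1). Converted to an odds ratio, d = 0.53 gives exp(0.53 × π/√3) = 2.62. Assumed, because the documents give none: control completion 30-80%; RCT with two-sided 5% alpha and 80% power.

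**Step 1: precision.** With control rate pc, the app-arm rate pt follows from the OR.

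- Half-width of the 95% CI for the difference = 1.96 × √[(pc(1−pc) + pt(1−pt))/40]
- SE of the log OR = √[1/(40·pc(1−pc)) + 1/(40·pt(1−pt))]

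At pc = 0.50 and OR 1.6, pt = 0.615, a difference of 11.5 points. The half-width is 1.96 × √[(0.250 + 0.237)/40] = 21.6 points. The SE is 0.453, so the OR interval is 1.6 × exp(±1.96 × 0.453), or 0.66 to 3.89.

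| Control | OR 1.0: half-width | OR 1.6: difference | OR 1.6: half-width | OR 2.62: difference | OR 2.62: half-width |
|---|---|---|---|---|---|
| 30% | 20.1 | 10.7 | 20.8 | 22.8 | 21.0 |
| 40% | 21.5 | 11.6 | 21.7 | 23.5 | 21.3 |
| 50% | 21.9 | 11.5 | 21.6 | 22.3 | 20.8 |
| 60% | 21.5 | 10.6 | 20.7 | 19.7 | 19.7 |
| 70% | 20.1 | 8.9 | 19.0 | 15.9 | 17.8 |
| 80% | 17.5 | 6.5 | 16.3 | 11.3 | 15.2 |

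Half-widths run from 15.2 to 21.9 points. At OR 1.6 the half-width exceeds the true difference at every control rate. At OR 2.62 the two are about equal: with 50% control the OR interval is about 1.03 to 6.6.

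**Step 2: what this could do to the RCT size.** This step adds the assumption that the crude observed rates are used as the RCT's planning rates. All 41 × 41 pilot outcomes were enumerated with their binomial probabilities. For each outcome with app completion above control, the size per arm was

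n = [1.96√(2p̄(1−p̄)) + 0.842√(pc(1−pc) + pt(1−pt))]² / (pt − pc)², with p̄ = (pc + pt)/2,

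rounded up and compared with n at the true rates. Outcomes with no benefit give no size and are counted separately.

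| Control | OR 1.6: n needed | >2-fold off | no size | OR 2.62: n needed | >2-fold off | no size |
|---|---|---|---|---|---|---|
| 30% | 314 | 52.9% | 18.7% | 72 | 43.4% | 2.3% |
| 40% | 288 | 56.1% | 17.4% | 70 | 40.4% | 2.1% |
| 50% | 290 | 55.9% | 17.5% | 74 | 45.6% | 2.4% |
| 60% | 317 | 54.3% | 18.8% | 85 | 45.4% | 3.3% |
| 70% | 379 | 53.0% | 21.5% | 106 | 48.2% | 5.3% |
| 80% | 520 | 50.4% | 26.4% | 151 | 48.3% | 9.5% |

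At OR 1.6, 33-38% of pilots give less than half the size needed and 12-22% more than twice. At OR 2.62 the shares are 18-26% and 23-25%. An RCT at half the needed size has about 51% power instead of 80%. Planning at 90% power barely changes the shares (50-56% and 41-48%). Without rounding n up, the OR 2.62 range is 41-51%.

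**The case against.** The strongest reply is that the plan never says the point estimate will be the assumed effect. It calls the effect size an indicator that informs the calculations, and the Study Summary speaks more broadly of pilot results. Nothing excludes using the interval, the control rate or outside evidence. This stands. A reader might infer that section 10.3 commits to sizing the RCT on the point estimate, and that 40-56% is the plan's failure rate. The documents support neither. The shares depend on two background effects that are not planning values, an assumed control range, unadjusted proportions where the plan has a logistic model that may include covariates, and a counting rule. Adding the no-size pilots raises the share at OR 1.6 to 72-78%; a true OR of 4.0 lowers the share without them to 29-42%.

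A reader might also infer that section 10.2 contradicts the cited screening trial. It does not say which previous studies it relies on, so that cannot be shown.

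Nor does it follow that the RCT must be sized on a fixed worthwhile difference and the pilot estimate barred. At 50% control, an illustrative 10-point difference needs 388 per arm and a 15-point difference 170, against 74 needed if the true OR is 2.62. Using the pilot only to check compatibility with such a difference would discriminate poorly: with no true effect, its 95% CI would still contain 10 points in 84% of pilots and 15 points in 71%. That choice is a trade-off for the investigators.

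None of this rescues the sentence in 10.2. It claims a property of this sample, and Step 1 tests it without assuming how the RCT will be planned.

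**Conclusion.** The point holds in this form. With 40 per arm, the 95% CI for the difference in completion is expected to reach about 15-22 points either side, for control completion of 30-80% and a true OR of 1 to 2.62. At OR 1.6 that is 16-22 points around a difference of 6.5-11.6. The pilot can yield an estimate, as section 2.1 asks, but it cannot be relied on to determine the effect, as section 10.2 says. Section 10.3 then passes the estimate on without asking for its uncertainty.

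The mis-sizing shares (50-56% at OR 1.6, 40-48% at OR 2.62, plus 17-26% and 2-10% with no size) are conditional illustrations of why that matters. They are not properties of the plan.

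**What to change.** **Section 10.2.** Replace the sentence on adequacy with:

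> With 40 per arm, the 95% CI for the difference in six-month completion is expected to extend about 15 to 22 percentage points either side of the estimate (assuming control completion of 30-80% and a true odds ratio between 1 and 2.6); the pilot is not expected to determine the effect precisely.

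If the investigators have a control rate from their own earlier work, it should replace the assumed range and the figures should be recomputed.

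**Section 10.3 and Statistical Methodology in the Study Summary.** Replace the two power-calculation sentences with:

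> The odds ratio from the logistic model, the unadjusted risk difference and the completion rate in each arm will be reported with 95% CIs. The future RCT will not be sized on the pilot point estimate alone; its power calculation will take account of the interval, for example through a conservative bound or a worthwhile difference set in advance.

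Which of these routes to take is left to the investigators.

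**Cost.** Wording only, with no new data, since completion is already recorded for every participant. The stated justification for 80 becomes less favourable, and the RCT may be larger than an optimistic pilot would suggest. A conservative bound has its own price. As an illustration over control rates of 20-80%, sizing on a one-sided 80% lower limit for the OR cuts the share of RCTs below half the needed size from 33-38% to 8-12% at OR 1.6. But 39-54% of pilots would then have a limit at or below 1 and give no size.

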## 11.0 STUDY MANAGEMENT

### 11.1 Conflict of Interest

Any research personnel who has a conflict of interest with this study (patent ownership, intellectual property, royalties, or financial gain greater than the minimum allowable by their institution, etc.) must declare their conflict of interest to the appropriate institutional review bodies. Local institutional conflict of interest policies will be followed for all research personnel associated with the research project.

### 11.2 Institutional Review Board (IRB) Approval and Consent

It is expected that the IRB will have the proper representation and function in accordance with federally mandated regulations. The IRB should approve the consent form and protocol.

In obtaining and documenting informed consent, the investigator should comply with the applicable regulatory requirement(s), and should adhere to Good Clinical Practice (GCP) and to ethical principles that have their origin in the Declaration of Helsinki.

Before recruitment and enrollment onto this study, the patient will be given a full explanation of the study and will be given the opportunity to review the consent form. Each consent form must include all the relevant elements currently required by the FDA Regulations and local or state regulations. Once this essential information has been provided to the patient and the investigator is assured that the patient understands the implications of participating in the study, the patient will be asked to give consent to participate in the study by signing an IRB-approved consent form.

Prior to a patient's participation in the trial, the written informed consent form should be signed and personally dated (in person or electronic via RedCAP) by the patient and by the person who conducted the informed consent discussion.

**11.3 Required Documentation**

N/A

**11.4 Registration Procedures**

All patients must be enrolled onto trial through the Cancer Clinical Trials Office Central Registration process. Prior to registration, a member of the study staff must scan and email the following documents as individual PDF files to the Central Registration Mailbox ([contact]) with a cc to the Central Registrars.

- Signed Informed Consent(s)
- Signed CCTO Registration Form
- Signed Eligibility Checklist
- Additional supporting documentation (i.e. lab/scan reports) may be included at the study teams' discretion.

The designated Central Registrar will review all received documents for consistency and completeness.

- If there is any concern or discrepancy noted, the study staff member who originated the central registration request will be contacted immediately for clarification.

If the patient is deemed eligible for study enrollment based on a thorough review by the Central Registrar, the patient will be entered into the CTMS system and a Registration Confirmation Letter is generated and sent to the following individuals:

- Study team
- Treating Physician
- Research Infusion Nurse designee
- Research Pharmacy

**11.5 Data Management and Monitoring/Auditing****11.5.1 Elements of a Data and Safety Monitoring Plan**

1. *List the name(s) of the individual(s) at the Icahn School of Medicine at Mount Sinai (ISMMS) who will be responsible for data and safety monitoring of this study. For each individual, indicate their role, name, title, and department information.*

ISMMS Principal Monitor:  
Principal Investigator

Last Name: [name]  
First Name: [name]  
Academic Title:  
Department: Oncological Sciences  
Mailing Address: [name]  
[contact]  
E-mail: [[contact]](mailto:[contact])

ISMMS Additional Monitor:  
Team Member

Last Name: [name]  
First Name: [name]  
Academic Title: MA  
Department: Population Health Science and Policy, Oncological Sciences  
Mailing Address: [name]  
[contact]  
E-mail: [[contact]](mailto:[contact])

2. *Justify your choice of principal monitor in terms of the assessed risk to the research subject's health and wellbeing.*

Participants could experience mild to moderate emotional discomfort from 1) failed attempts to use the App, 2) engaging with an App that is focused on colorectal cancer 3) breach in confidentiality. In the event a patient requires a higher level of care or assistance than provided in this study, a Licensed Clinical Psychologist ([name], PI) will be consulted and the participant will be referred to the appropriate level of care. If additional intervention is necessary, [name] will coordinate with Mount Sinai's Psychiatry Department.

As per ISMMS PPHS policies, the PI is required to notify PPHS of any unanticipated problems involving risks to participants or others that occur. If an adverse event is due to the intervention and is unexpected, the PI will draft a safety report and send a copy to PPHS. The PPHS committee will serve as an objective review mechanism. This policy/procedure means that any potential conflict of interest inherent in the PI being the sole reviewer of serious adverse events is avoided.

3. *List the specific items that will be monitored for safety (e.g., adverse events, subject compliance with the protocol, drop outs, etc.).*

- Informed Consent
- Subject compliance with the protocol
- Research Staff compliance with the protocol
- Adverse Events
- Drop outs

4. *Indicate the frequency at which ACCUMULATED safety and data information (items listed in number 3 above and interim analysis of efficacy outcomes) will be reviewed by the monitor(s) or the Data Monitoring Committee (DMC). Although this information must be reviewed at least annually, the higher the study risks, the more frequently reviews must be scheduled.*

The PI will monitor the progress of the trial and the safety of participants on an ongoing basis. The procedures of this study, such as regular meetings with research staff and the entire study team, will ensure prompt discussion and reporting of all study conduct issues, including adverse events. During these meetings, the PI will focus on participant safety by reviewing adverse events, study progress (e.g. recruitment, retention, protocol adherence), data integrity and study outcomes. Additionally, we anticipate that risk-benefit ratio will remain favorable throughout the study. However, if at any point it is not, we will stop the study and re-evaluate study procedures in order to ensure a positive risk-benefit ratio for participants.

The table below describes each data monitoring activity, responsible staff person, and frequency of review. Tracking forms will be developed to document the occurrence of all reviews. The PI will review all reports as they are generated.

Activity	Report	Timing of review
Informed Consent	Quality control of each new consent by Research Coordinators	PI reviews all consents upon receipt
Protocol Adherence (both Subjects and Research Staff)	Weekly report generated by Research Coordinators	Weekly PI review

Adverse Events	Weekly report generated by Research Coordinators	Weekly PI review
Study Retention	Weekly report generated by Research Coordinators	Weekly PI review
Review of Medical Charts to Assess Colonoscopy Completion Status	Weekly report generated by Research Coordinators	Weekly PI review
Self-Report Information	PI and other study staff will review all self-report materials and complete fidelity checklist	PI will review data weekly for completeness and accurate entry into a database for analysis

5. *Where applicable, describe rules which will guide interruption or alteration of the study design.*

N/A

6. *Where applicable, indicate dose selection procedures that will be used to minimize toxicity.*

N/A

7. *List any specialized grading system that will be used to evaluate adverse events (e.g., National Cancer Institute Common Toxicity Criteria).*

The severity of an adverse event is graded as follows:

- Mild (grade 1): the event causes discomfort without disruption of normal daily activities.
- Moderate (grade 2): the event causes discomfort that affects normal daily activities.
- Severe (grade 3): the event makes the patient unable to perform normal daily activities or significantly affects his/her clinical status.
- Life-threatening (grade 4): the patient was at risk of death at the time of the event.
- Fatal (grade 5): the event caused death.

8. *Describe procedures that will be used to assure data accuracy and completeness.*

Study data will be entered by a Research Coordinator trained to enter data into a password-protected, secure database on REDCap. To ensure the validity and integrity of study data, the PI will oversee all data management responsibilities. Data entry, level of accuracy and percentage of error in data entry will be discussed with the study team on a regular basis. Monthly meetings (either in person or via video/telephone conference) will be held with the entire study team.

Thorough training of Research Coordinators is also designed to ensure adequate protection of human subjects. All Research Coordinators will receive all required training and certification in Mount Sinai's human subjects in research. Research Coordinators will be required to participate in a training program designed to ensure that they administer the interviews and evaluate participant responses in a sensitive manner. Research Coordinators will be trained to speak clearly and audibly and let participants determine the pace of the interview.

Protocol compliance will be monitored at the weekly research staff meetings. The PI will meet with the study staff on a weekly basis to train and ensure adherence to the intended protocol. The PI will be responsible for updating all investigators regarding any study related issues that arise of that need to be addressed.

The medical chart abstraction will be conducted by a research team member. A second research team member will review 20% of the medical charts to confirm accuracy.

9. *Should a temporary or permanent suspension of your study occur, in addition to the PPHS, to whom (NIH, FDA, sponsor, IRB) will you report the occurrence?*

IRB and Program Officer of the National Institute On Aging/NIH/DHHS

